4.1.1 Treatment overview (Cohorts 1 & 2)

After being consented, patients will undergo baseline evaluations including clinical exam, complete blood count, blood chemistry, and thyroid function test. Baseline core or surgical biopsy and images with either CT scan or MRI scan will be obtained at screening. Blood collection for correlative analyses will be performed anytime after consent and prior to Nivolumab administration. Nivolumab 480mg will be administered intravenously on approximately Day -28 prior to planned surgery on Day 0 to Day +14 (14 day window as needed for scheduling surgery/logistics). An earlier surgery date is permissible if clinically indicated – see section 4.1.2 (salvage treatment).

Patients will undergo post-treatment images and specimen collection ideally within 7 days from planned surgery date, or as clinically indicated.

Post-operative adjuvant treatment with radiotherapy or chemoradiotherapy can be delivered, if clinically indicated at the discretion of treating physician following the standard of care. All subjects will

Johns Hopkins Protocol #: J1923

get follow up imaging about 3 months after completion of curative therapy (e.g. after adjuvant therapy) as per clinical routine.

After the initial post-treatment images, further imaging will be obtained as clinically indicated. In case of recurrence, a biopsy will be obtained and the specimen will be secured for future analyses if clinically feasible.

To explore oral and gut microbial correlates of response to neoadjuvant nivolumab, stool samples and oral rinses will be collected at baseline prior to infusion and then again prior to surgery. Subjects will also be asked to fill out a medical, antibiotic use and dietary questionnaire that will be used to assess whether antibiotic use or dietary patterns correlate with features of the oral and gut microbiome.

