Never drank after age 40 _____

Currently aged less than 40 years _____

MEDICAL QUESTIONS

23. Have you taken antibiotics in the last 3 months? Yes No

A list of antibiotics is attached for you to refer to. If no, skip to question 25.

24. If you know the name of the antibiotic(s), please write it here.

25. Have you had a bronchoscopy in the last 3 months? Yes No

26. Have you taken oral corticosteroids in the last 2 weeks? Yes No

(Oral corticosteroids examples: prednisone, dexamethasone, methylprednisolone, hydrocortisone)

27. If you answered Yes to (26), please write the name and dose here and when you took these.

28. Have you taken inhaled corticosteroids in the last 2 weeks? Yes No

(Inhaled corticosteroids examples: budesonide, fluticasone, beclomethasone, ciclesonide)

29. If you answered Yes to (28), please write the name and dose here and when you took these.

30. Do you have sleep apnea? Yes No

31. Do you have reflux disease? Yes No

32. Do you have any other chronic lung conditions? Yes No

33. If you answered Yes to (32), please write the name of the condition here

DENTAL HEALTH

34. About how often do you visit a dentist?

- Less than every 6 months.
- Between every 6-12 months.
- Greater than every 12 months.
- I have never been to a dentist.

35. Overall, how would you rate the health of your teeth and gums?

Excellent Good Fair Poor

36. Have you ever had treatment for gum disease such as scaling and root planing, sometimes called deep cleaning? Yes No

37. Have you ever had any teeth become loose on their own, without an injury? (Not including baby teeth). Yes No

DIET QUESTIONS

38. Do you eat meat? Meat is defined as beef, chicken, pork, lamb or venison:

- A. I do not eat meat.
- B. I have eaten meat in the last year.
- C. I have eaten meat one or more times a month during the last year.
- D. I have eaten meat one or more times a week during the last year.

39. Do you eat Fish? Fish is defined as all fish and shellfish:

- A. I do not eat fish.
- B. I have eaten fish in the last year.
- C. I have eaten fish one or more times a month during the last year.
- D. I have eaten fish one or more times a week during the last year

40. Do you eat Eggs?

- A. I do not eat eggs
- B. I have eaten eggs in the last year
- C. I have eaten eggs one or more times a month during the last year
- D. I have eaten eggs one or more times a week during the last year

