41. Do you eat Cheese? (This includes fresh, soft, aged or cottage cheese as well as sour cream):

- A. I do not eat cheese
- B. I have eaten cheese in the last year
- C. I have eaten cheese one or more times a month during the last year
- D. I have eaten cheese one or more times a week during the last year

42. Do you drink Milk? Milk is defined as milk from a cow, goat or sheep (not soy, coconut or almond milk, for example). If you put milk on your cereal, you should not answer (A).

- A. I do not drink milk
- B. I drank milk in the last year
- C. I drank milk one or more times a month during the last year
- D. I drank milk one or more times a week during the last year

43. Do you eat yogurt?

- A. I do not eat yogurt
- B. I have eaten yogurt in the last year
- C. I have eaten yogurt one or more times a month during the last year
- D. I have eaten yogurt one or more times a week during the last year

44. Do you take probiotics (live bacteria supplement)? Yes No

If yes (question 44) and if you know the name of the probiotic product(s), please write here:

45. Do you take vitamin supplements?

Yes No

If yes (question 45) and if you know the name of the vitamin supplement(s), please write it/them here:

WORK AND PHYSICAL ACTIVITY

46. What is your current employment status?

Employed/self-employed Unemployed Retired Disabled

47. How would you categorize your physical activity on the job?

Mostly sedentary or light activity (e.g. mostly sitting, standing, lifting light objects of less than 3 kilos).

Mostly medium activity (e.g. much walking, climbing stairs).

Mostly intense activity (e.g. heavy construction work).

Unemployed/retired/disabled

48. What type of exercise (physical activity) do you do regularly (at least 3 times per week)?

Mostly moderate activity (slow walking, gardening, golfing etc.)

Mostly vigorous activity (running, swimming, bicycling, football etc.)

I do not exercise regularly

49. At age 20, what type of exercise did you do regularly (at least 3 times per week)?

Mostly moderate activity (slow walking, gardening, golfing etc.)

Mostly vigorous activity (running, swimming, bicycling, football etc.)

I did not exercise regularly

Follow-Up Sociodemographic Characteristics Questionnaire

Date: Month _____ / Day _____ / Year _____
Study ID Number: _____
Medical Records Number: _____

SMOKING QUESTIONS

1. Are you currently smoking? Yes No

If yes, how many cigarettes/day? _____

ALCOHOL QUESTIONS

2. Regularly? Yes No

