If yes, please indicate pattern:

More than one per week _____ (If checked), please indicate number _____

Less than one per week _____

MEDICAL QUESTIONS

3. Have you taken antibiotics since completing the last questionnaire? Yes No

4. If you know the name of the antibiotic(s), please write it here.

A list of antibiotics is attached for you to refer to. If no, skip to question 5.

5. Have you had a bronchoscopy since completing the last questionnaire? Yes No

6. Have you taken oral corticosteroids since completing the last questionnaire? Yes No
(Oral corticosteroids examples: prednisone, dexamethasone, methylprednisolone, hydrocortisone)

7. If you answered Yes to (6), please write the name and dose here and when you took these.

8. Have you taken inhaled corticosteroids since completing the last questionnaire?

Yes No (Inhaled corticosteroids examples: budesonide, fluticasone, beclomethasone, ciclesonide)

9. If you answered Yes to (8), please write the name and dose here and when you took these.

DIET QUESTIONS

10. Do you eat meat? Meat is defined as beef, chicken, pork, lamb or venison:

- A. I do not eat meat.
- B. I have eaten meat in the last year.
- C. I have eaten meat one or more times a month during the last year.
- D. I have eaten meat one or more times a week during the last year.

11. Do you eat Fish? Fish is defined as all fish and shellfish:

- A. I do not eat fish.
- B. I have eaten fish in the last year.
- C. I have eaten fish one or more times a month during the last year.
- D. I have eaten fish one or more times a week during the last year

12. Do you eat Eggs?

- A. I do not eat eggs
- B. I have eaten eggs in the last year
- C. I have eaten eggs one or more times a month during the last year
- D. I have eaten eggs one or more times a week during the last year

13. Do you eat Cheese? (This includes fresh, soft, aged or cottage cheese as well as sour cream):

- A. I do not eat cheese
- B. I have eaten cheese in the last year
- C. I have eaten cheese one or more times a month during the last year
- D. I have eaten cheese one or more times a week during the last year

14. Do you drink Milk? Milk is defined as milk from a cow, goat or sheep (not soy, coconut or almond milk, for example). If you put milk on your cereal, you should not answer (A).

- A. I do not drink milk
- B. I drank milk in the last year
- C. I drank milk one or more times a month during the last year
- D. I drank milk one or more times a week during the last year

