15. Do you eat yogurt?

- A. I do not eat yogurt
- B. I have eaten yogurt in the last year
- C. I have eaten yogurt one or more times a month during the last year
- D. I have eaten yogurt one or more times a week during the last year

16. Do you take probiotics (live bacteria supplement)? Yes No

If yes (question 16) and if you know the name of the probiotic product(s), please write here:

17. Do you take vitamin supplements? Yes. No

If yes (question 17) and if you know the name of the vitamin supplement(s), please write it/them here:

WORK AND PHYSICAL ACTIVITY

18. What type of exercise (physical activity) do you do regularly (at least 3 times per week)?

- Mostly moderate activity (slow walking, gardening, golfing etc.)
- Mostly vigorous activity (running, swimming, bicycling, football etc.)
- I do not exercise regularly

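### The six follow-up food items keep the baseline one-year look-back, so their frequency options cannot show a current or partial diet change when the post-surgical and later microbiome samples are taken

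*Combined protocol and SAP*

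**What the plan says.** Section 4.1.1 gives the questionnaire its purpose: it "will be used to assess whether antibiotic use or dietary patterns correlate with features of the oral and gut microbiome". Exploratory objective 4 in Section 1.2 concerns the gut and oral microbiota before and after nivolumab and their relation to pathologic response.

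The study calendar (Section 4.10) marks the medical and dietary questionnaire at Day -28, at the post-surgical evaluation (Days 21 to 42), at the follow-up visits and at recurrence. Stool and oral rinse are marked at each of these too, with the rinse optional at the first- and second-year follow-up visits.

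In Appendix D, the initial form has six food items (38 to 43) and the follow-up form repeats them (10 to 15). Options B to D refer to the past year on both forms. Examples are "I have eaten meat one or more times a week during the last year", "I have eaten cheese one or more times a week during the last year" and "I have eaten yogurt one or more times a week during the last year". Option A is a present-tense statement that the food is not eaten.

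Other follow-up items were adapted for repeat use. The antibiotic item asks "Have you taken antibiotics since completing the last questionnaire", and the bronchoscopy and corticosteroid items use the same interval. The probiotic item asks about current use: "Do you take probiotics (live bacteria supplement)? Yes No". The vitamin item does likewise.

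**The concern.** A repeated diet question is useful beside a repeated sample only if its answer can change when diet changes. A one-year look-back asked again a few weeks later mostly re-asks the baseline question. Sections 4.5 and 4.6 describe resection, reconstruction and possible radiotherapy or chemoradiotherapy of the head and neck, so a change in eating between the two forms is foreseeable. If the form does not register it, the diet variable paired with the post-surgical and later samples describes mainly pre-treatment eating. The correlation planned in Section 4.1.1 would then be blurred for those samples.

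**Working it through.** The plan gives no figure for this point, so there is nothing to reproduce. The check is the share of each follow-up reference year that the baseline answer already covers.

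**Inputs**
- Look-back of options B to D on both forms: one year, taken as 365 days (Appendix D).
- Baseline form: Day -28 (Section 4.10).
- Post-surgical form: Days 21 to 42 (Section 4.10). If these days are counted from surgery on Day +14, the latest is Day 42 + 14 = Day 56.
- Follow-up visits: every 3 to 4 months in year 1, then every 6 months. I count these from Day 0 and take 3, 4 and 6 months as 91, 122 and 183 days (assumption).

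**Formula**

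Days since baseline: e = visit day + 28. Overlap with the baseline year = (365 − e)/365, with a minimum of 0.

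| Form | e (days) | Overlap with baseline year | Share after Day -28 |
|---|---|---|---|
| Post-surgical, Day 21 | 49 | 316/365 = 87% | 13% |
| Post-surgical, Day 42 | 70 | 295/365 = 81% | 19% |
| Post-surgical, Day 56 | 84 | 281/365 = 77% | 23% |
| Follow-up, 3 months | 119 | 246/365 = 67% | 33% |
| Follow-up, 4 months | 150 | 215/365 = 59% | 41% |
| Follow-up, 6 months | 211 | 154/365 = 42% | 58% |
| Follow-up, 12 months | 393 | 0% | 100% |

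Successive follow-up forms also overlap each other: (365 − 91)/365 = 75% at a 3-month gap, (365 − 122)/365 = 67% at 4 months and (365 − 183)/365 = 50% at 6 months.

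**What this does to one answer**

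Take a patient who ate yogurt weekly until surgery on Day 0 and then stopped. At the post-surgical form, 21 to 42 of the past 365 days are without yogurt, which is 6% to 12% of the year. The weekly option still describes the remaining 88% to 94%, so the patient can truthfully tick the box ticked at baseline. Option A is also true, because the patient no longer eats yogurt. Two patients with the same history can therefore give opposite answers. A patient who cut down from weekly to occasional intake has no option that shows it.

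**After the change**

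A 2-week look-back at the post-surgical form lies wholly within the 49 or more days since baseline, so overlap with the baseline year is 0%. Asking about the interval since the previous form also gives 0%, with a window of 49 to 70 days (up to 84).

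**The case against.** The strongest reply is that Section 4.1.1 speaks of dietary patterns, and a one-year recall is a defensible way to describe habitual diet. That stands for the baseline form. It does not justify repeating the question unchanged at each visit, when the same follow-up form resets its antibiotic, bronchoscopy and corticosteroid items to the interval since the last form.

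Several stronger readings are tempting, but the documents do not support them.

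- **That the follow-up form cannot register any diet change.** Option A is in the present tense and can record complete avoidance. The probiotic and vitamin items ask about current use. What is lost is current frequency and partial change, together with the ambiguity between A and the past-year options.
- **That diet change after surgery confounds the main before/after comparison.** Section 4.1.1 describes samples before infusion and again before surgery, and later eating cannot affect a pre-surgical sample. The calendar marks stool but no questionnaire at the pre-surgical evaluation, so rewording the follow-up form would not supply a diet record for that sample either. The point concerns the post-surgical and later samples.
- **That an unrecorded diet change would be credited to nivolumab.** The microbiome tests in Section 11.2.2 compare responders with non-responders. No test attributing a before/after shift to the drug is planned.
- **That the corticosteroid items will show a spurious rise in use.** The look-back does change, from "Have you taken oral corticosteroids in the last 2 weeks" to "Have you taken oral corticosteroids since completing the last questionnaire". But both forms then ask for name, dose and when the drug was taken, so a 2-week window can be recovered where those dates are completed.

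The aim is exploratory in about 26 patients. That limits the weight of the point, but the correction is also small.

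**Conclusion.** The point holds as a minor improvement to an exploratory aim. At the first follow-up form, 81% to 87% of the reference year is shared with baseline (77% on the latest reading of the visit days), and 59% to 67% is still shared at 3 to 4 months. Overlap with baseline ends only once 365 days have passed since Day -28. Even then the answer is a one-year recall and does not describe diet at the time of the sample. Options B to D are therefore a poor measure of diet for the samples collected beside them, which weakens the Section 4.1.1 correlation for those visits.

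This assumes that the calendar's questionnaire is the Appendix D form, with the initial version at Day -28 and the follow-up version from the post-surgical visit on. It also assumes that patients read the past-year options literally. The documents do not allow an estimate of how many patients would change diet or how they would answer, so the effect on the correlation itself cannot be sized.

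**What to change.** In the follow-up form, change items 10 to 15 to a short fixed period before the sample, for example the past 2 weeks, with frequency options that fit that period. At the least, ask about the interval since the previous form, as the medical items already do. The fixed period is better because its length stays the same at every visit.

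Add matching short-period items to the initial form and keep its one-year items for habitual diet. State in Section 11.2.2 that the short-period answers will be used in the diet-microbiome analysis of samples collected at the same visit.

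The cost is revised wording, about six extra baseline items and IRB approval of the form. Patients already enrolled would have no short-period baseline answers, so their change from baseline could not be assessed on the new items. No visit, sample or endpoint changes.
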